6.4.3.4 Hemostat Application

The prescribed hemostatic agent will be applied according to the respective product Instructions for Use. Any device malfunctions will be recorded on the Device Malfunctions eCRF using FDA CDRH (Center for Devices and Radiological Health) Event Reporting nomenclature.²³ This will be a single-blinded trial. The subjects will be blinded as to the hemostatic treatment received. Unblinding will be permitted after a subject has completed his or her 6 week follow-up visit evaluation.

The anatomic site is defined as the approximate surface area of bleeding site, measured by multiplying the greatest perpendicular distances of the bleeding site. The anatomic application site is defined as the approximate surface area of the target application site, measured by adding one (1) centimeter to both greatest perpendicular distances of the bleeding site and multiplying the two values. The anatomic site and anatomic application site must meet all intraoperative eligibility criteria noted in Section 6.4.3.2. The anatomic site must not exceed 25cm². The anatomic application site must not exceed 47cm². Anatomic site and anatomic application site will be calculated and documented for the bleeding site on the Operative eCRF.

NOTE: The actual resection site may be larger than the anatomic site and/or anatomic application site (e.g., a liver resection site may be 5 inches by 4 inches, however you will only be allowed to evaluate investigational product on a 25cm² anatomic site).

The investigator will be allowed to use the entire contents of up to two 5 gram bellows of PerClot per investigational subject. Each box of PerClot supplied will contain five separate packages. Only two 5 gram bellows (packages) can be used per subject. Sites will be instructed to bring two packages of PerClot and two packages of the control product into the operating room on the day of the surgery. Application of investigational product will be addressed during investigator training. The exact amount of investigational product applied will be determined by weighing the device(s) before and after use.

The site of bleeding should be thoroughly covered with the granules. It is important that the PerClot granules come into direct contact with the bleeding surface. Gentle manual pressure will be applied until hemostasis is achieved in accordance with Appendix A: PerClot Instructions for Use and Appendix N: Operative Steps; any gauze used when applying pressure must be carefully removed for hemostasis evaluation. Wetting of the gauze with saline will facilitate this process. If gauze is adhered to the formed blood clot, the gauze should be fully saturated with saline, and then gently and slowly peeled away.

Gentle manual pressure using dry gauze will be applied immediately after application and held for 5 minutes. Gentle manual pressure using dry gauze will be re-applied after the 5 minute hemostatic assessment point and held until the 7 minute evaluation. If at the 7 minute evaluation, hemostasis is achieved, the surgeon will continue to observe the site for an additional 5 minutes (12 minutes post-application) to assess for hemostasis

maintenance. If, at any time after the 7 minute evaluation, hemostasis is not achieved or maintained, the surgeon will be allowed to use alternative measures to control bleeding.

Time of device application will be documented.

The Arista IFU will be followed for the application of control product. Application of Arista will also be addressed during investigator training and in the Operative Steps (Appendix N). The amount of hemostatic product applied in each subject will be determined by recording the mass in grams of the device(s) before and after application.

The surgeon will also be asked to estimate the amount of device left in the patient in relation to the original amount applied (percentage) after saline irrigation and aspiration of excess material, if applicable. The amount of irrigation fluid used during the irrigation and aspiration of excess material will be documented. Dislodgement of RSD, during gauze removal, will be assessed at the 5 minute and 7 minute hemostatic evaluations. The surgeon will document if the dislodgement is perceived to be the sole reason for any observed hemostatic failure. If hemostasis is observed at 7 minutes, maintenance of hemostasis will be assessed for an additional 5 minutes (12 minutes post-application) and again just prior to surgical closure.

Information regarding hemostat application will be documented on Operative eCRF.

6.4.3.5 Intraoperative Evaluations and Assessment of Hemostasis

All subjects will undergo the same intraoperative investigation evaluations unless otherwise stated. Intraoperative is defined as the time interval from when the subject enters the surgical suite until the subject exits the surgical suite. Hemostatic evaluation time points will be measured on a continuum with time zero being the time of hemostat application. The treated bleeding site will be observed and evaluated at each of the pre-defined time points regardless of when hemostasis is achieved. For example, if hemostasis is achieved at 5 minutes, the surgeon will still evaluate the application site at 7 minutes to ensure that hemostasis has been maintained. If hemostasis is observed at 7 minutes, an assessment will be made to ensure hemostasis maintenance for an additional 5 minutes (12 minutes post-application) and again just prior to surgical closure.

Success/failure criteria will be defined as follows:

- If the surgeon visually observes complete cessation of bleeding, this will be considered successful hemostasis;
- If the surgeon visually observes bleeding egressing from the RSD, this will be considered a failure of hemostasis;

If hemostasis is not achieved at 7 minutes after test or control hemostat application, the surgeon may use alternative means necessary to achieve hemostasis (i.e., other approved and marketed hemostatic devices for the applicable therapeutic area). Additionally, if hemostasis is achieved at 7 minutes after test or control hemostat application, but is not maintained at any point during the additional 5 minute observation period (12 minutes post-application) or bleeding is observed at the target application site just prior to closure, the surgeon may use alternative means necessary to achieve hemostasis (i.e., other approved and marketed hemostatic devices for the applicable therapeutic area). Any alternative

means used to achieve hemostasis will be documented. The test or control hemostat will not be allowed to be re-applied after the 7 minute hemostatic evaluation time point.

A sample Operative Worksheet is attached as Appendix F; this worksheet will assist in the collection of intraoperative data and will act as the source document for intraoperative evaluations. All intraoperative data will be recorded.

The following intraoperative parameters will also be collected after the 7 minute hemostasis endpoint and prior to closure:

- Diastolic and systolic blood pressure;
- Pulse;
- Core body temperature; and
- Use of any blood modifiers, insulin, or blood sugar lowering medications.

Other data to be collected intraoperatively include:

- Surgical procedure(s) to be performed, including any concomitant procedures;
- Placement of a drain and time of placement, if applicable;
- Total operative time (from skin incision to skin closure);
- Total intraoperative estimated blood loss;
- Hemodilution (i.e. crystalloids, colloids, urine output, other);
- Intraoperative blood products administered (i.e. red blood cells, platelets, fresh frozen plasma, cryoprecipitate);
- Use of blood modifiers, insulin, or blood sugar lowering medications and other products known to affect bleeding or glucose levels;
- Other topical hemostatic agents used during procedure, if applicable;
- The incidence of any device malfunctions;
- NNIS Risk Index;
- The incidence of any complications/adverse events; and
- The incidence of any deviations from protocol.

Once the subject is randomized to a treatment group and undergoes hemostatic agent application and intraoperative evaluations, the Operative eCRF must be completed and the Product Accountability Log updated. The screening and enrollment log should also be filled out to document if a subject satisfies the eligibility criteria. A draft screening and enrollment log is provided in Appendix D.

6.4.4 Postoperative Evaluations

All subjects will undergo the following assessments within 24 hours postoperatively:

- Clinical signs or symptoms of bleeding;
- Any blood product administration;
- Reoperation;
- Use of any blood modifiers insulin, or blood sugar lowering medications or reversal drugs;
- Drainage volume within the first 24 hours postoperatively and time of drain volume measurement, as applicable;

- Complete blood count, coagulation status (platelet count, PTT, INR, and fibrinogen) and Complement C3;
- Incidence of any complications/AEs;
- Clinical signs or symptoms of embolism or thrombosis; and
- Thromboembolism Assessment.

All subjects will undergo a blood glucose assessment at the following time points:

- After randomization (prior to application of study device);
- Within 1 hour following study device application;
- 6 hours (\pm 30 min) following study device application;
- 12 hours (\pm 30 min) following study device application; and
- 24 hours (\pm 30 min) following study device application.

Note: Blood glucose measurements should be evaluated with venous blood draw or the Nova StatStrip blood glucose meter. Blood glucose measurements should not be evaluated with any other blood glucose meter.

The Postoperative eCRF and Laboratory eCRF must be completed for the postoperative evaluation. The Blood Modifiers/Insulin or Blood Sugar Lowering Medications eCRF, Adverse Event eCRF, and Reoperation eCRF should also be completed as applicable.

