2.1 Description and Intended Use

PerClot is a medical device composed of absorbable polysaccharide granules and delivery applicators. The granules are biocompatible, non-pyrogenic, and derived from purified plant starch. The granules do not contain any human or animal components. PerClot granules have a molecular structure that rapidly absorbs water, forming a gelled adhesive matrix that provides a mechanical barrier to further bleeding and results in the accumulation of platelets, red blood cells, and coagulation proteins (thrombin, fibrinogen, etc.) at the site of application. One gram of PerClot absorbs at least 19 mL of water. The gelled adhesive matrix thus promotes the normal physiological clotting cascade. PerClot granules are enzymatically degraded by alpha-amylase and glucoamylase and by macrophages. Based on preclinical studies, absorption normally requires several days and is dependent on the amount of material applied on the wound and the site of use.

The intended use for PerClot in this clinical investigation will be in surgical procedures as an adjunctive hemostatic device when control of capillary, venular, and arteriolar bleeding by pressure, ligature, and other conventional procedures is ineffective or impractical.

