6.1.3 Endpoints

The primary efficacy endpoint of this investigation is the achievement of hemostasis for the treated bleeding site at 7 minutes following the application of the prescribed hemostatic agent. The secondary efficacy endpoint for this investigation is hemostasis for the treated bleeding site at 5 minutes.

The safety endpoints will consist of:

- Total operative time;
- Hemostasis at 5 and 7 minutes;
- Hemostasis maintenance;
- Total intraoperative estimated blood loss;
- Alternative means required to achieve hemostasis (where applicable);
- Units of blood transfused intraoperatively and postoperatively (where applicable);
- Incidence of reoperation;
- Total hospitalization time;
- The incidence of procedure complications; and
- The incidence of adverse events through final follow-up, including, but not limited to:
 - Adhesions or fibrosis;
 - Anaphylaxis;
 - Blockage of the bladder or ureteral lumen;
 - Blockage of the bypass system;
 - Cancer recurrence and/or progression;
 - Compromised attachment of prosthetic devices to bone or tissue;
 - Death;
 - Embolism;
 - Failure of deep or superficial wound healing;
 - Failure to obtain hemostasis;
 - Fever;
 - Hemorrhage;
 - Infection;
 - Peri-operative hyperglycemia;
 - Exacerbation of surgical procedure-associated adverse events;
 - Swelling and compression of pressure-sensitive tissues and structures;
 - Thromboembolism;
 - Thrombosis; and
 - Toxicity.

Any procedure complications/adverse events through final follow-up will be reported as per Common Terminology Criteria for Adverse Events (2009): CTCAE-2009.²²

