6.2 Investigational and Comparator Devices

6.2.1 *PerClot – Investigational Device*

Please refer to Section 2.

6.2.2 *Comparator Devices*

When a subject is randomized to the control group, he or she will receive Arista on the qualified bleeding site. This hemostatic agent was chosen as the control because it is a medical device, as is PerClot, is plant-based, and does not contain any pharmaceutical components such as thrombin or fibrinogen. Arista has a comparable indication for use as the intended use of PerClot for this clinical trial, and thus would not limit its use in this investigation.

Arista is a medical device intended for application to surgical wound sites as an absorbable hemostat. This technology incorporates hydrophilic, flowable, microporous particles synthesized by cross-linking purified plant starch through a proprietary process; Arista is a 100% plant based polysaccharide. Arista contains no human or animal components. Arista is a fine, dry, sterilized white powder that is biocompatible, non-pyrogenic, and is typically absorbed within 24 to 48 hours.

Arista particles are hydrophilic molecular sieves that enhance natural hemostasis by concentrating blood solids such as platelets, red blood cells, and blood proteins on the particle surfaces to form a gelled matrix. The concentrated gel matrix provides a barrier to further blood loss and is formed regardless of the patient's coagulation status. The concentration of clotting factors and platelets in the gel serves to enhance normal clotting reactions and creates stable hemostatic plugs. The absorption process begins immediately and is dependent on several factors, including the amount applied and site of use.

The use of Arista as the control in this investigation has been approved by FDA.

6.2.3 *Other Medical Devices*

[figure not shown]

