6.4.5 Discharge Evaluation

Discharge evaluations will occur at hospital discharge or between 24 hours and 14 days postoperatively. Discharge evaluations consist of:

- Clinical signs or symptoms of bleeding;
- Reoperation;
- Use of any blood modifiers, insulin, or blood sugar lowering medications or reversal drugs;
- Total hospitalization time;
- Incidence of any complications/AEs;
- Drainage volume, as applicable;
- Time of drain volume measurement, as applicable;
- Time of drainage removal, as applicable; and
- Deep Vein Thrombosis (DVT) prophylaxis methods and duration.

The Discharge eCRF must be completed at discharge. The Blood Modifiers/Insulin or Blood Sugar Lowering Medications eCRF, Adverse Event eCRF, and Reoperation eCRF should also be completed as applicable.

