A medical professional, usually a physician, under whose direction an investigational device is administered.

Ischemia

Lack of delivery of oxygen and other nutrients to tissue.

Ligation

Tying a duct or blood vessel with a ligature.

Local tissue necrosis or injury

Morphological changes indicative of cell death and caused by the progressive degradation action of enzymes. It may affect groups of cells or part of a structure or an organ.

Monitor

Person employed by the Sponsor or CRO who reviews study records to determine that a study is being conducted in accordance with the protocol. A monitor's duties may include, but are not limited to, helping to plan and initiate an investigation, and assessing the conduct of investigations. Monitor work with the clinical research coordinator to check all data and documentation from the investigation. See also Clinical Research Associate (CRA).

Monitoring

Reviewing a clinical investigation, ensuring conduct, proper records and reports are performed as stated in the clinical protocol, standard operating procedures, GCP and by regulatory requirements.

National Nosocomial Infections Surveillance (NNIS) System

An ongoing collaborative surveillance system sponsored by the Centers for Disease Control (CDC) to obtain national data on nosocomial infections.

Overall Survival

An assessment to determine whether a patient is alive or deceased..

Patient

Individual seeking medical care.

Postoperative

The time interval from skin closure until hospital discharge.

Preclinical testing

Before a drug or device may be tested on humans, preclinical studies must be conducted either *in vitro* but usually *in vivo* on animals to determine that the drug or device is safe.

Preoperative Form

A form designed to collect the required protocol information obtained during the preoperative period.

Principal Investigator

An individual responsible for the conduct of the clinical investigation at an investigational site. In the event the investigation is conducted by a team of individuals at the investigational site, the Principal Investigator is the responsible leader of the team.

Protocol

A detailed plan that sets forth the objectives, study design, and methodology for a clinical trial. A study protocol must be approved by an IRB before investigational drugs or devices may be administered to or used in humans.

Protocol Amendment

Changes or clarifications made in writing to the original protocol.

PTT

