b. Systolic: mmHg59. Core body temperature: °C58. Pulse: beats/min60. Use of any blood modifiers, insulin, or blood sugar lowering medications? ₁ Yes ₀ No*If yes, please complete the Blood Modifiers / Insulin or Blood Sugar Lowering Medications Form. Refer to Appendices K & L For Complete List.*61. Placement of Drain: ₁ Yes ₀ No *If yes, time of drain placement (24-hour clock) (HH:MM):* : 62. Prior to closure assess if the treated bleeding site maintained hemostasis ₁ Yes ₀ No

ADDITIONAL HEMOSTATIC MEASURES

63. If hemostasis has not maintained prior to closure, what alternative means of achieving hemostasis were used (check all that apply):

 a. StitchesIf checked, specify # of stitches: b. Manual pressure appliedIf checked, specify time (minutes): c. Other hemostatic deviceIf checked, specify: d. OtherIf checked, specify: e. No additional actions were taken or products used Not applicable

Operative DRAFT Form
Form 3H

Form completed by: _____
Date form completed: ___ / ___ / ___

Subject Initials:

PerClot® - The C.L.O.T. Investigation

Subject Number: Visit Type: Intraoperative

AFTER COMPLETION OF OPERATIVE PROCEDURE

64. Total operative time (skin incision to skin closure): minutes65. Estimated total blood loss: mL

66. Other Hemodilution:

a. Colloids: mLb. Crystalloids: mLc. Urine output: mLd. Other, please specify: mL

67. Intraoperative blood products:

Red Blood Cells Units Fresh Frozen Plasma UnitsPlatelets Units Cryoprecipitate Units68. Use of any blood modifiers, insulin, or blood sugar lowering medications? 1 Yes 0 No*If yes, please complete the Blood Modifiers/ Insulin or Blood Sugar Lowering Medications Form. Refer to Appendices L & K for Complete List.*69. Please list any other topical hemostatic agents used during procedure: 0 No other topical hemostatic agents used**Record Blood Glucose (mg/dL) within one hour following device application on Laboratory Form.****Note: Blood glucose measurement should be evaluated by a venous blood draw or Nova StatStrip blood glucose meter.**

Subject Initials: Subject Number: Visit Type: 3 Intraoperative

CALCULATION OF NATIONAL NOSOCOMIAL INFECTIONS SURVEILLANCE (NNIS)*†

70. The patient's procedure is classified as (select one):

0 Clean
 1 Clean-Contaminated
 2 Contaminated
 3 Dirty

Table 1. Physical Status Classification for Surgical Patients *‡

Class I	A normally healthy patient
Class II	A patient with mild systemic disease
Class III	A patient with severe systemic disease

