- h. Device damaged prior to use (FDA Source Code 2284)
- i. Inability to irrigate (FDA Source Code 1337)
- j. Inaccurate delivery (FDA Source Code 2339)
- k. Occlusion (obstruction or blockage) within device or device component (FDA Source Code 2423)

 1 Yes	 0 No
 1 Yes	 0 No
 1 Yes	 0 No
 1 Yes	 0 No
 1 Yes	 0 No
 1 Yes	 0 No
 1 Yes	 0 No
 1 Yes	 0 No
 1 Yes	 0 No
 1 Yes	 0 No
 1 Yes	 0 No
 1 Yes	 0 No

l. Other, please specify:

*Please include FDA
Source Code*

*Device malfunctions will be reported using nomenclature specific to devices per the FDA Center for Devices and Radiological Health Event Reporting webpage: <http://www.fda.gov/MedicalDevices/Safety/ReportaProblem/EvenProblemCodes/ucm/134751.htm>.

INTRAOPERATIVE ADVERSE EVENTS

75. Did any complications/adverse events occur intraoperatively?

1 Yes *If yes, please complete the Adverse Event Form.*
 0 No

76. Please list any known intraoperative deviations to the protocol:

0 Not applicable

77. Additional comments:

0 Not applicable

/ / /

Principal Investigator Signature

Date (DD/MMM/YYYY)

Subject Initials: Subject Number: Visit Date (DD/MMM/YYYY): / / Visit Type: 4 Postoperative

POSTOPERATIVE ASSESSMENT

1. Does the subject have clinical signs or symptoms of bleeding?

1 Yes *If yes, please complete the Adverse Event Form.*
 0 No

2. Did the subject undergo a reoperation?

1 Yes *If yes, please complete the Reoperation Form.*
 0 No

3. Blood products administered postoperatively: Blood Product Units

 1 None	Red Blood Cells	 
	Platelets	 
	Fresh Frozen Plasma	 
	Cryoprecipitate	 

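### Postoperative transfusion is an endpoint with no time limit, but units are scheduled for collection only to 24 hours, so units given from then to discharge are not reliably captured

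*Protocol*

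**What the plan says.** The endpoint list in Protocol 6.1.3 includes "Units of blood transfused intraoperatively and postoperatively (where applicable"; the closing words only limit it to patients for whom it applies. The same item is in the Synopsis, in Protocol 6.6.4 and in SAP sections 1 and 4.4.4. None of these states a time window. The Glossary (Protocol section 13) defines postoperative as "The time interval from skin closure until hospital discharge".

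On collection, Protocol 6.4.4 opens with "All subjects will undergo the following assessments within 24 hours postoperatively", and blood-product administration is one of the items that follow. Table 3 in Protocol 6.4.7 and Table 1 of the SAP give the Postoperative visit the same 24-hour window. The matching field is item 3 of the sample Postoperative Form in Appendix E, "Blood products administered postoperatively". It takes units of red cells, platelets, fresh frozen plasma and cryoprecipitate, or none.

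The next visit is in Protocol 6.4.5: "Discharge evaluations will occur at hospital discharge or between 24 hours and 14 days postoperatively. Discharge evaluations consist of" a list that has no blood-product item.

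**The concern.** The endpoint covers the period to discharge on the Protocol's own definition, while the schedule that feeds it stops at 24 hours. A patient taken back to the operating room on day 3 for bleeding at the application site and given several units would have a Reoperation Form, but nowhere on it to enter those units.

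The Protocol itself treats transfusion as important: section 3 names blood-product administration and its adverse effects among the reasons for wanting a better hemostat. The gap also looks unintended. Signs of bleeding and reoperation are asked at 24 hours, at discharge and at 6 weeks, and drain volume at 24 hours and again at discharge. Transfusion stops at 24 hours, and no reason is given. The risk is a safety table labelled postoperative that mostly contains 24-hour data.

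**Working it through.** The documents give no transfusion figure to reproduce, so the check traces the endpoint through each place that could hold units.

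| Collection point | Blood-product units? |
|---|---|
| Protocol 6.4.3.5; Operative Form item 67 | Yes, for the operation |
| Protocol 6.4.4; Postoperative Form item 3 | Yes; visit within 24 hours |
| Protocol 6.4.5; Discharge Form | No |
| Protocol 6.4.6.1; Follow-Up Form | No |
| Reoperation Form | No; asks the reason, the hemostatic methods used and whether the device was visible |
| Adverse Event Form | No units field; free text under action taken |
| Blood Modifiers form | A drug list; Appendix L has some plasma derivatives (albumin, factor concentrates) but not red cells, platelets, fresh frozen plasma or cryoprecipitate |

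From the 24-hour visit to discharge, then, no scheduled item or form field asks for units. Missing-data rules do not fill the gap: Protocol 6.6.13 and SAP 4.8 set an analysis for the primary endpoint only.

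Size, by illustration. Let *s* be the share of a patient group's postoperative units given after the 24-hour assessment. If nothing later is recorded,

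recorded total = (1 − *s*) × true total.

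- *s* = 10%: 1 − 0.10 = 90% recorded
- *s* = 30%: 1 − 0.30 = 70% recorded
- *s* = 50%: 1 − 0.50 = 50% recorded

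The values of *s* are assumptions; the documents give none.

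For the comparison between arms, write each arm's units as early (to 24 hours) plus late. The recorded difference is early PerClot minus early Arista; the late terms drop out. A difference in units that arises only after 24 hours cannot appear in this endpoint if the form is completed as scheduled.

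**The case against.** The best defence is that "postoperative" is also a visit name. Table 3 and SAP Table 1 use it for the 24-hour visit, the SAP has no glossary, and the Glossary is not always the working definition: it runs intraoperative from skin incision to closure, while Protocol 6.4.3 uses entry to and exit from the surgical suite. Item 3 of the Postoperative Form carries no hour limit, although item 6a on the same form does, so a site could read item 3 as running to discharge. Appendix E also says that the forms are only examples.

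Part of this stands. It shows that the window is ambiguous, and that some sites might record later units. It does not close the gap: the omission is in the visit lists of the Protocol body as well as on the forms, and sites reading item 3 differently would make the total inconsistent. If 24 hours was intended, neither document says so where the endpoint is defined.

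A reader might also draw stronger conclusions that the documents do not support:

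- **Late transfusions are entered as zero.** No rule says so. They are not asked for, and so would generally add nothing.
- **The delayed-bleeding signal is lost.** Bleeding signs and reoperation are asked at discharge and at 6 weeks, re-hospitalization at 6 weeks and drainage at discharge. Hemorrhage is a listed adverse event, and Protocol 9.2 asks for the treatment of each event. Only the units are missing.
- **Different absorption times make late bleeding the place to look.** The Protocol says that for PerClot "absorption normally requires several days and is dependent on the amount of material applied" and that Arista "is typically absorbed within 24 to 48 hours", but it links neither to late bleeding. Two of its animal studies (3.2.1 and 3.2.2) detected neither product at the implant site at 24 hours.
- **The gap favours a non-inferiority claim.** Non-inferiority is tested only on hemostasis at 7 and 5 minutes. SAP 4.4.4 calls the safety analyses descriptive.
- **The intraoperative count is also wrong because it includes units given before the device.** The item "Intraoperative blood products" collects what the endpoint names, and randomization balances earlier units in expectation.
- **The share of hours covered measures the loss.** With an assumed day-5 discharge, 24/120 = 20% of hours are covered; at day 14, 24/336 = 7%. These are shares of time, not of units, and day 14 is a visit limit rather than a length of stay.

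**Conclusion.** The mismatch is real. Followed as written, the plan does not reliably capture units given between the 24-hour assessment and discharge, and it under-counts an endpoint that it states without a limit. The shortfall equals the unknown share *s*. This conclusion rests on the Glossary meaning of postoperative and on sites completing the Postoperative Form at its scheduled visit. On the narrower reading, where the endpoint is meant to stop at 24 hours, the counts would be right and the label incomplete, so one of the two still needs changing.

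The reach is limited to one descriptive safety line. The primary analysis, the sample size and the type I error are untouched. Nothing in the documents shows that the under-count differs between arms.

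**What to change.** Add blood products given since the 24-hour assessment (units of red cells, platelets, fresh frozen plasma and cryoprecipitate) to Protocol 6.4.5 and the Discharge Form. Count to the actual discharge date, since the discharge visit has its own window, and include any units given at a reoperation. State in Protocol 6.6.4 and SAP 4.4.4 that postoperative units are summarized by arm from skin closure through discharge.

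If the later data cannot be recovered from charts, rename the endpoint in both documents as units transfused during surgery and within 24 hours after it.

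The cost is a few chart-abstraction fields, with no new visit or test. The reported transfusion figure may rise.
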